9.2 Serious adverse event

An SAE is any unexpected medical occurrence that:

- Results in death;
- Is life-threatening, i.e in this context refers to an AE in which the participant was at risk of death at the time of the AE; it does not refer to an AE that hypothetically might have caused death if more severe;
- Results in persistent or significant disability or incapacity, i.e. the AE resulted in a substantial disruption of the participant’s ability to conduct normal activities;
- Requires in-patient hospitalization or prolongation of existing hospitalization (note: this clinical trial does not have any period of scheduled hospitalization), i.e. the AE requires at least an overnight admission or prolongs a hospitalization beyond the expected length of stay. Hospital admissions for surgery planned before study entry, for social reasons, for any elective surgery (i.e. plastic surgery) or for normal disease management (including treatment adjustment) are not to

be considered as SAE according to this criterion (i.e. if the protocol or the standard management of the disease under study requires planned hospitalization);

- Congenital anomaly/birth defect, i.e. an AE outcome in a child or fetus of a participant exposed to the IMP (or marketed medicinal product (Note: only to be added for marketed drug)) before conception or during pregnancy;
- Important medical event, i.e. is medically significant. Medical and scientific judgment should be exercised in deciding whether other situations should be considered serious events/reactions, such as important medical events that might not be immediately life-threatening or result in death or hospitalization but might jeopardize the participant or might require intervention to prevent one of the other outcomes listed above. Examples of such medical events include allergic bronchospasm requiring intensive treatment in an emergency room or at home, blood dyscrasias or convulsions that do not result in in-patient hospitalization, or the development of drug dependency or drug abuse.

9.3 Adverse event of special interest

An AE (serious or non-serious) of scientific and medical concern specific to the Sponsor's product or program, for which ongoing monitoring and rapid communication by the investigator to the Sponsor may be appropriate. Such an event may require further investigation to characterize and understand it. For this study, no predefined AE of special interest is listed since the investigational drug is a well-known treatment.

9.4 Eliciting Adverse Event information

The investigator is required to report all directly observed AE and all AE spontaneously reported by the trial participant, using concise medical terminology. In addition, during each trial visit, the participant will be interviewed using a checklist and will undergo a physical exam for AE evaluation.

9.5 Adverse Event reporting period

The AE reporting period for this trial begins upon administration of the first dose of trial medication at Day 1 for non-serious events; or upon participant enrolment in the trial (after signature of informed consent) for serious events. This period finishes at the end of patient participation in the trial. All AE that occurs during the AE reporting period specified in the protocol must be reported in the CRF, when considered treatment related. In addition, any SAE that occurs after the AE reporting period, and which is assessed by the investigator as related to the investigational medication should also be reported as an AE.

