9.1 Adverse event definition

AE is defined as any unexpected medical occurrence in a participant or clinical trial participant after the administration of a pharmaceutical product and which does not necessarily have a causal relationship with the treatment. AE include worsening (in severity and frequency) of pre-existing conditions ("Medical history") before the first Investigational Medicinal Product (IMP) administration and abnormalities of procedures (e.g. EKG) or laboratory results which are assessed as "clinically significant".

Laboratory / procedure abnormalities considered as AE

Laboratory / procedure abnormalities (or worsening in severity or frequency of pre-existing abnormalities)

assessed as “clinically significant” must be reported as an AE only if they meet at least one of the following conditions:

- The abnormality suggests a disease and/or organ toxicity AND this abnormality was not present at the screening visit or is assessed as having evolved since the screening visit;
- The abnormality results in discontinuation of the study drug;
- The abnormality requires medical intervention or concomitant therapy.

When reporting an abnormal laboratory/procedure result, a clinical diagnosis should be recorded rather than the abnormal value itself (for example, “anemia” rather than “decreased red blood cell count”).

What is not an AE?

- Medical conditions present at the initial study visit that do not worsen in severity or frequency during the study are NOT considered as AE;
- Symptoms, exacerbation or worsening of the studied disease will NOT to be considered as AE nor captured on the AE page of the CRF if consistent with the anticipated natural progression of the disease (overall and for this given participant);
- Lack of efficacy of the investigational product is NOT considered as AE.

The investigator or appropriate site personnel will examine any participant experiencing an AE as soon as possible. The investigator will do whatever is medically necessary for the safety and well-being of the participant.

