The participant will remain under observation as long as a participant is receiving trial drug, and for two months following the last day of drug administration, or longer if medically indicated in the opinion of the investigator. All AEs observed or reported following administration of IMP will be followed until resolved or until medically stable. All AE identified will be assessed for seriousness, severity, and causality and recorded in the appropriate AE section of the CRF using standard medical terminology to avoid the use of vague, ambiguous, or colloquial expressions.

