10.9 Safety Analysis

Safety analyses will include all participants who have received at least one dose of the study medication. The proportion of participants with SAE, AESI and/or AEs leading to treatment discontinuation will be described per study arm and by System Organ Class (using preferred terms defined by MedDRA 13.1), according to the CTCAE, version 5. The proportion of participants presenting at least one AE will be described. Participants with multiple events with the same preferred terms will be counted once. The maximum severity grade for each preferred term and body system will be summarized. If multiple events with the same preferred terms are recorded for a participant, the event with the maximum grade will be

included in the analysis. In addition, a narrative for each of the SAEs and AESI will be developed detailing all aspects related to the medical event. AEs not leading to treatment discontinuation will also be described per study arm using the same classification as presented above.

Incidence rate and 95% confidence interval will be presented per study arm will be presented for SAE and AEs per category and most frequent AEs. Otherwise only descriptive statistics will be presented.

Safety laboratory parameters (hematology and biochemistry) will also be described individually per study arm, showing the proportion of participants by degree of elevation relative to ULN and to baseline values and clinical significance, and blood levels changes over time. Shift tables will be presented. A listing of participants experiencing lab parameters elevation will be included.

EKG abnormalities will be described per treatment arm as the proportion of participants per type of EKG finding, clinical relevance and changes over time. Participants with altered EKG may have an echocardiogram to evaluate cardiac involvement or cardiac progression of CD.

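### Section 9.5 restricts CRF recording to treatment-related AEs, contrary to sections 9.1, 9.4, 9.6 and 9.8, and the schedule shows no AE evaluation at any follow-up visit

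*Protocol*

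**What the plan says.** Section 9.5 opens the reporting period at the first dose for non-serious events and at consent for serious ones. On its end it says: "This period finishes at the end of patient participation in the trial". It then states that AEs in that period "must be reported in the CRF, when considered treatment related".

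Other sections set no such condition:

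- Section 9.1: "All AE identified will be assessed for seriousness, severity, and causality and recorded in the appropriate AE section of the CRF".
- Section 9.4: "The investigator is required to report all directly observed AE and all AE spontaneously reported by the trial participant".
- Section 9.6 sends non-serious AEs to the CRF, and SAEs to the AE CRF as well as the SAE form.
- Section 9.8 has the investigator rate every serious and non-serious AE as related or not related.

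On the analysis side, section 10.9 promises: "The proportion of participants presenting at least one AE will be described". It also promises a description by arm of AEs that did not stop treatment, and incidence rates with 95% confidence intervals for SAEs and AEs. The secondary endpoint in section 3, AEs leading to treatment discontinuation, carries no causality condition.

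On timing, sections 3.2 and 9.4 have participants asked about AEs at each visit. The AE row of the schedule in section 12 is marked at days 14, 28 and 56 and at the unscheduled AE visit only. Sections 8.5 and 8.6, which list what is done at the follow-up and end-of-study visits, do not mention AE evaluation.

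The definitions use an odd word. Section 9.1: "AE is defined as any unexpected medical occurrence in a participant". Section 9.2: "An SAE is any unexpected medical occurrence that".

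**The concern.** This is a rule about what is collected, so no statistical analysis plan can repair it. An AE left out of the CRF because the investigator thought it unrelated is not there to be counted, re-coded or re-classified at analysis. Section 9.5 is also where site staff would naturally look to learn what to report and when.

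If some sites work from 9.5 and others from 9.1 or 9.4, the AE database will mix related events only with all events. The all-AE proportions and rates in section 10.9 would then partly reflect which section a site happened to follow.

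The gap in the schedule adds a timing problem. A site that uses section 12 as its checklist has no prompt to collect AEs after day 56, while the reporting period continues until the participant leaves the trial.

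**Working it through.** No stated figure is in dispute, so the check is a comparison of the text, followed by a test of how far the consequence reaches.

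**1. Is there a reading that reconciles 9.5 with the other sections?**

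| Place | Condition for entry in the CRF |
|---|---|
| 9.5 | related AEs only |
| 9.1 | all AEs, each assessed for causality |
| 9.4 | all observed and all spontaneously reported AEs |
| 9.6 | non-serious AEs and SAEs, no condition |
| 9.8 | every AE rated, with not related as one of two ratings |
| 12, footnote 5 | repeats the start of the period, no condition |

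Under 9.5 the not-related rating in 9.8 would have almost nothing to apply to. Section 9.5 also fails on its own terms. It starts the SAE period at consent, before any dose, when no event can be drug related. Its last sentence uses relatedness to limit which SAEs are reported after the period ends, a distinction with little purpose if the same limit already holds within it. No reading reconciles the clause with the rest.

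**2. Which events are exposed if 9.5 is followed?**

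- SAEs: covered by the unconditional rule in 9.6.
- AEs that stop treatment: section 9.12 requires the reason for discontinuation in the source and CRF, section 10.7 reports reasons for drop-out by arm, and section 9.1 makes a clinically significant laboratory or procedure abnormality that stops the drug a reportable AE. The reason survives even where the AE entry might not, so this endpoint is largely protected.
- Non-serious AEs judged unrelated that did not stop treatment: no other safeguard. These feed the at-least-one-AE proportion and the AE incidence rates in 10.9.

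**3. Timing.** The scheduled visits after baseline are days 14, 28 and 56 (3 visits) and months 1, 4, 6, 8, 12, 18 and 24 after end of treatment (7 visits), 10 in all. The AE row marks 3 of the 10 and none of the 7 follow-up visits. The 9.5 period covers all 10.

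**4. Does the clause weaken the discontinuation comparison?** Section 10.1 assumes 20% against 10%, with 224 per arm. Using the normal approximation at two-sided 0.05,

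power = Φ[(d − 1.96·se0)/se1], with se0 = √(2·p̄(1−p̄)/n) and se1 = √((p1(1−p1)+p2(1−p2))/n).

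Full capture: p̄ = 0.15, se0 = √(0.255/224) = 0.0337, se1 = √(0.25/224) = 0.0334, power = Φ(1.01) = 0.845. The protocol gives no capture fraction or background rate, so the rows below rest on assumed values.

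| Assumption | Rates | Power |
|---|---|---|
| all captured | 20% v 10% | 0.845 |
| 90% captured in both arms | 18% v 9% | 0.798 |
| 80% captured in both arms | 16% v 8% | 0.742 |
| 50% captured in both arms | 10% v 5% | 0.520 |
| 2% unrelated background kept in both arms | 22% v 12% | 0.807 |
| 5% unrelated background kept in both arms | 25% v 15% | 0.755 |

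Losing genuine drug events lowers power. Keeping truly unrelated background events also lowers it, so filtering those out would not. The direction depends on which events are dropped, and the documents do not settle that.

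**The case against.** The strongest answer is that one trailing clause stands against several unconditional rules, and a site reading the whole of section 9 would record everything. Section 10.3 also names the superiority outcome as adverse drug reactions, for which related events are all that is needed. The first part limits the consequence: a filtered record arises only where 9.5 is followed. It does not remove the defect, since the clause is an explicit instruction in the section that governs reporting. The second part does not rescue it either. Related events can always be selected from a full record, while the all-AE summaries in 10.9 cannot be rebuilt from a filtered one.

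A reader might infer more than the documents support:

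- *That the safety comparison between arms is biased.* Investigators are blinded (section 6.7), and all arms take tablets for 8 weeks on one visit schedule (sections 6.1 and 12). Nothing shows that the filter would act differently by arm.
- *That section 9.1 sets a third collection window.* The phrase "for two months following the last day of drug administration" describes how long the participant stays under clinical observation, or longer if indicated. It is not a recording cut-off, so ratios of person-time built on it or on the schedule marks have no basis in the protocol.
- *That the definitions exclude known benznidazole reactions.* Section 6.9.1 treats hypersensitivity reactions as AEs and section 6.9.3 has neutropenia reported as an SAE, so the intent is clear. The word is wrong, but it is not a second filter.
- *That the DSMB loses the chance to re-judge causality.* Its stated purpose in sections 4.1 and 10.3 is the 12-month data and the decision on interrupting an arm. No such role is given.

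**Conclusion.** The contradiction is real and section 9.5 is wrong as written. Where 9.5 is followed, the permanent loss is mainly of non-serious AEs judged unrelated that did not stop treatment. The at-least-one-AE proportion and the AE incidence rates by arm in section 10.9 would then be incomplete and might not be comparable between sites. SAEs and the discontinuation endpoint are largely protected, and neither bias between arms nor a direction of effect on power is shown. The number of lost events cannot be sized from the protocol.

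The timing mismatch also stands, between the 9.5 period with the every-visit enquiry in 3.2 and 9.4 on one side, and the schedule with 8.5 and 8.6 on the other. It bears on events after treatment and hardly on the discontinuation endpoint, which can arise only during the 8-week course. The change should be made, and promptly, because events not entered are not recoverable.

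**What to change.** 1. In section 9.5, delete the clause on treatment relatedness, so that every AE in the period is entered and relatedness is kept as the rating given under section 9.8.
2. Reconcile the AE row of section 12 and the visit contents in sections 8.5 and 8.6 with the reporting period in section 9.5, so that one collection window applies in all arms.
3. As a minor wording correction, replace *unexpected* with *untoward* in the definitions in sections 9.1 and 9.2.

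The cost is protocol wording, a note to sites and a few more CRF entries per participant. No dose or clinical management rule changes.

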9.6 Adverse Event reporting requirements

Information on AE must be evaluated by a physician. Each AE is to be classified by the investigator as

serious or non-serious. This classification will determine the reporting procedure for the event. All SAE are to be reported immediately (within 24 hours of awareness of the SAE by the investigator) to the study PI, using the SAE report form. This includes a description of the event, onset date and type, duration, severity, relationship to trial drug, outcome, measures taken, and all other relevant clinical and laboratory data. The initial report is to be followed by the submission of additional information (follow-up SAE form) as it becomes available. Any follow-up reports should be submitted as soon as possible, but within 5 working days.

SAE should also be reported on the clinical trial AE CRF. It should be noted that the SAE form is not the same as the AE section of the CRF. Although the same data are collected, the two forms must be completed in a consistent manner, and the same medical terminology should be used. Any other additional reporting requirement will be addressed in the trial manual.

Non-serious AE are to be reported in the CRF. In the CRF, a given AE will be recorded only once per participant, and the severity recorded should be the maximum level reached. If several distinct episodes of the same condition occur, their number will be recorded in the CRF. In addition to immediately reporting SAEs to the Sponsor, investigators are responsible for reporting SAEs occurring at their site to their Independent Ethics Committee (IEC), and any periodic safety reporting, following the local requirements of their institution.

9.7 Grading of Adverse Event severity

Severity is a clinical determination of the intensity of an AE. The severity for an AE should be graded using the National Cancer Institute's Common Terminology Criteria for Adverse Events (CTCAE, version 5.0)⁵, defining the System Organ Class (using preferred terms defined by MedDRA 13.1). In case of AEs that are not described in the CTCAE v5.0, the investigator will use the terminology MILD, MODERATE, or SEVERE to describe the maximum severity of the AE as follows:

- **MILD** Does not interfere with the patient's usual functions;
- **MODERATE** Interferes to some extent with the patient's usual functions;
- **SEVERE** Interferes significantly with the patient's usual functions.

This information on AE grading will be entered in the AE section of the CRF. It is to be noted the distinction between severity and seriousness of AE. An SAE is not necessarily a serious event.

9.8 Adverse Event causality assessment

For both serious and non-serious AE, the investigator is required to assess the potential relationship between the AE and the trial drug, i.e. to determine whether there exists a reasonable possibility that the trial drug caused or contributed to the AE.

⁵ https://ctep.cancer.gov/protocoldevelopment/electronic_applications/docs/ctcae_v5_quick_reference_5x7.pdf

To help investigators with the decision binary tree in the evaluation of causality, investigators will be asked to consider the following before reaching a decision:

- Medical history;
- Lack of efficacy / worsening of existing condition;
- Trial medications;
- Other medications (concomitant or previous);
- Withdrawal of trial medication, especially following trial discontinuation / end of trial medication;
- Erroneous treatment with trial medication (or concomitant);
- Protocol related procedure.

The relationship of an AE to investigational treatment is assessed and determined by the investigator after careful consideration of the event in terms of biological plausibility, possible unrelated causes, any pre-existing medical conditions or concomitant medications, temporal relationship between administration of investigational treatment and the onset (or worsening) of the event and known patterns of response to trial medications in general. The causality assessment of an AE to the investigational medicinal product will be rated as follows:

- Not related: There is no reasonable possibility of causal relationship;
- Related: There is at least a reasonable possibility of a causal relationship between an AE and an IMP. This means that there are facts (evidence) or arguments to suggest a causal relationship.

The decision to suspend and resume treatment or to permanently interrupt treatment due to an AE will be left to the trial clinician in charge. The clinician should take into consideration the Assessment of Safety defined for this protocol and the rules for permanently interrupting trial treatment.

9.9 Exposure *in utero*

In this trial, women of childbearing age must have a negative serum pregnancy test at screening, should not be breastfeeding, and should use a double method of contraception to avoid pregnancy during exposure to the study drugs and up to three months after completion of the treatment. Women who are using oral, implanted, or injectable contraceptive hormones or mechanical products such as an intrauterine device with a hormonal component are required to use an additional barrier method of contraception for the period specified. To assure that requirement, health professional should explain the teratogenic risk and future implications for the fetus and family as a whole in case of getting pregnant within the treatment period. In the event that the participant does not use any contraceptive method, barrier contraceptives will be provided by the research team. If any trial participant becomes or is found to be pregnant while receiving any of the study treatment drugs (or during study post-treatment follow-up period +3 months), the medication must be interrupted, and the investigator must submit the event on a 'Clinical Study Pregnancy Report Form' together with the first day of the last menstruation period and the expected date of birth. This must be done irrespective of the occurrence of an AE. The information submitted should include the anticipated date of delivery. The investigator will follow the participant until completion of the pregnancy or until pregnancy termination (i.e., induced/spontaneous abortion). The

investigator will provide pregnancy outcome information in a ‘Clinical Study Pregnancy Outcome Report Form’.

Note: A pregnancy is not an SAE. Any unfavorable outcome meeting a seriousness criterion, i.e., in the case of unfavorable pregnancy outcome (miscarriage, stillbirth), birth defects, or congenital abnormalities, the incident will be reported using the SAE form (in addition to the Pregnancy Outcome Form).

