5.1 Eligibility criteria

5.1.1 Inclusion Criteria

- Adults aged ≥ 18 years;¹
- CD diagnosis through the positivity of two serological tests that use different antigens (recombinant and native antigens, according to World Health Organization (WHO) recommendations) (28).
- Informed consent form read and signed by the participant.
- Weight ≥ 50 kg to ≤ 95 kg.
- Ability to carry out all tests and visits to the protocol site and have a fixed address.
- Women of childbearing age should have a negative urine or serum pregnancy test at baseline.

¹ It is considered that neither the dynamics of parasitemia, nor the therapeutic response and safety profile, demonstrate differences in the chronic phase adult population up to 60 years of age. Considering that there is no contraindication for administering antiparasitic treatment beyond 60 years of age, and that the objective is to see the antiparasitic effect and the safety profile, recruiting patients older than 60, which will allow a greater probability of recruiting patients in the shortest possible time, optimizing studytimes, financial resources, and the opportunity to have the results available.

A contraceptive method should be used.²

Note that although PCR will be determined at baseline, this will not be considered as an inclusion criterion.

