5.1.2 Exclusion Criteria

- Currently pregnant, breastfeeding³ or expressing gestational desire for the next 2 months.
- Previously received treatment with BZN or NFX (either completely or incompletely);
- Any concomitant use or documented history of using allopurinol or antifungals (ketoconazole, itraconazole and posaconazole);
- History of hypersensitivity, allergic or SAE to any “nitroimidazole”, and/or its components;
- Acute or chronic health problems that, in the informed opinion of the investigator, may interfere with the evaluation of the efficacy and/or safety of the drug. Examples are acute infections, Human Immunodeficiency Virus (HIV) infections, liver disease with liver failure and kidney disease requiring support treatment;
- Signs and/or symptoms of severe cardiac form of CD⁴;
- History of cardiomyopathy, heart failure or severe ventricular arrhythmia of any etiology;
- Alcoholic participants or those with a history of alcohol abuse (considered as intake of >4 drinks on any single day AND >14 drinks per week for men and >3 drinks on any single day AND >7 drinks per week for women);
- Have basic laboratory parameters outside the normal range or parameters that are considered clinically relevant by the physician responsible for the participant;
- Participation in another clinical trial over the past 12 months.

Pregnancy will be considered an exclusion criterion. There is a strong recommendation for not treating pregnant women due to the possibility of teratogenic effects (experiments performed in animal models). There are inconsistent data regarding chronic Chagas disease during pregnancy; some studies showed increased risk of pregnancy loss, prematurity, and neonatal mortality while other studies did not. Since pregnancy data are inconsistent and chronic Chagas disease is generally not life-threatening, use of this

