² A subject will be considered fertile if, in the opinion of the researcher, she is biologically capable of having children and is sexually active. Women who are not fertile must meet at least one of the following criteria: have undergone a documented bilateral hysterectomy and/or oophorectomy; Have clinically confirmed ovarian insufficiency; have reached the postmenopausal state, defined as: cessation of regular menstruation for at least 12 consecutive months without alternative pathological or physiological cause. All women of childbearing age should be advised of the risk of teratogenesis and should use barrier contraceptives during the 60-day period of treatment (may additionally maintain other preferred contraceptive methods that are eventually in use).

³ The amount of this drug excreted into milk is much lower than the amount used to treat infants. Therefore, the use of this drug in nursing mothers who receive an indication of treating Chagas disease might be considered acceptable due to low drug levels in breastmilk and safety when given directly to infants. However, in those cases a close follow up of the newborns is recommended to detect and treat any adverse events. For the purpose of the clinical trial, we consider excluding these women since will add a complexity and a responsibility that could not be covered by the study.

⁴ Cardiac involvement will be assessed through clinical interview, physical examination, and electrocardiogram (EKG). Patients with abnormal EKGs (other rhythms than sinus rhythm, right or left bundle branch block, hemiblocks, ventricular extrasystoles, any heart conduction disorders etc.) will undergo an echocardiogram.

drug is not recommended due to risk of embryofetal toxicity.

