6.8 Concomitant medication

Participants may receive concomitant therapy for medical occurrences during the study. Medications that are considered necessary for the participant's welfare may be prescribed at the discretion of the investigator. However, specific drugs that elevate liver enzymes, are immune-suppressants or are known to have activity against *T. cruzi* should be avoided during the treatment phase of the study. It is requested that women of childbearing age do not initiate contraceptive drugs (pills, injection, implant, or patch) during the 60 days of study drug administration, as these may also be associated with increased liver enzymes (contraception will be avoided with barrier contraceptives). However, contraceptives can be maintained in those women who were already using them prior to the clinical trial. Although it is not a formal exclusion criterion, it is recommended not to take herbal medicines, food supplements and energetic drinks during the treatment period. In case of doubt patients should be advised to ask for permission to its physician. The PI should be contacted in case of any questions regarding concomitant medications.

All concomitant medications taken by the participant during the study, from the date of signature of the informed consent until the last study follow-up visit, will be recorded in the appropriate section of the CRF.

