8.3 Treatment visit

Three regular visits will be required during the treatment period, at 2, 4 and 8 weeks after the start of treatment. During each visit, the participant will be asked about the appearance of AE. If the researcher considers that such signs and symptoms are related to the drug (BZN), all measures that the researcher deems necessary will be carried out. Each case will be assessed individually and depending on severity and causality, treatment may be withdrawn definitively, suspended momentarily or concomitant medication may be administered.

- Visit at 2 weeks (+/- 2 days): Directed anamnesis and physical examination. Analytical extraction (hematology, biochemistry. Evaluation of AE and changes in concomitant medication. At this visit, the 1st kit of medications (BZN or placebo) will be collected, and the 2nd kit will be distributed to the participant.
- Visit at 4 weeks (+/- 2 days): Directed anamnesis and physical examination. Evaluation of AE and changes in concomitant medication. At this visit, the 2nd kit of medications (BZN or placebo) will be collected, and the 3rd kit will be distributed to the participant.
- Visit at 8 weeks (+/- 7 days): Directed anamnesis and physical examination. Extraction of laboratory tests (hematology, biochemistry. Evaluation of AE and changes in concomitant medication. In this visit the 3rd kit of medications (BZN or placebo) will be collected.

EQ-5D-3L and cost-effectiveness questionnaires will be distributed to and completed by the participant during each visit.

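### The eligibility text covers pregnancy prevention for about two months, while section 9.9 asks for double contraception for about five

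*Protocol*

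**What the plan says.** Pregnancy prevention is addressed in four parts of the protocol.

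- **Section 5.1.1, inclusion criteria.** The list says "A contraceptive method should be used". Its footnote 2 adds that women of childbearing age "should use barrier contraceptives during the 60-day period of treatment (may additionally maintain other preferred contraceptive methods that are eventually in use").
- **Section 5.1.2, exclusion criteria.** Besides current pregnancy and breastfeeding, a woman is excluded if she is "expressing gestational desire for the next 2 months".
- **Section 6.8, concomitant medication.** "It is requested that women of childbearing age do not initiate contraceptive drugs (pills, injection, implant, or patch) during the 60 days" of study drug. Methods already in use may continue.
- **Section 9.9, exposure in utero.** Women of childbearing age "should use a double method of contraception to avoid pregnancy during exposure to the study drugs and up to three months after completion" of treatment. Users of hormonal methods, including a hormonal intrauterine device, must add a barrier for that same period. Staff are to explain the risk to the fetus "in case of getting pregnant within the treatment period". For a woman using no method, "barrier contraceptives will be provided by the research team".

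No text links the eligibility rules to section 9.9 or says which prevails.

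**The concern.** The rules differ in length and in number of methods. Section 9.9 sets a protection period that continues for three months after treatment. The eligibility text, from which sites enrol, is built around the treatment period alone, and so is the counselling sentence within section 9.9 itself.

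This matters because the protocol cites possible teratogenicity and embryofetal toxicity as its reason for excluding pregnant women, and section 5.3 names women of childbearing age as a recruitment group. The schedule in section 12 places pregnancy tests at screening and at end of treatment, so none falls within the three months afterwards. A woman can therefore be properly enrolled while openly planning a pregnancy that section 9.9 asks her to avoid. This is a question of participant safety and of consistency within the protocol, not of inference.

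**Working it through.** The plan gives no figure to reproduce. The check is a comparison of the rules, with calendar arithmetic for the size of the gap.

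**Inputs**
- Blinded dosing lasts 8 weeks (56 days) in every arm, because placebo fills the shorter regimens (section 6.1).
- The last visit of the treatment period is described as "Visit at 8 weeks (+/- 7 days): Directed anamnesis and physical examination" (section 8.3), so the last dose is taken to fall on day 49 to 63.
- Assumed conversions: three months = 91 days; two months = 61 days, counted from day 0.

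**End of the section 9.9 period** = last dose + 91 days
- 49 + 91 = 140; 56 + 91 = 147; 63 + 91 = 154.
- 147 / 30.4 = 4.8 months from day 0.

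**Part lying beyond the pregnancy-intent exclusion** = end of period − 61
- 140 − 61 = 79; 147 − 61 = 86; 154 − 61 = 93 days.

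**Part left out of footnote 2**
- If its 60 days simply mean the dosing period: 91 days.
- If they mean literal day 60: 140 − 60 = 80; 147 − 60 = 87; 154 − 60 = 94 days.

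**Counting from the last active dose instead.** Active drug ends at week 2, 4 or 8, that is day 14, 28 or 56.
- Day 60 is already 60 − 14 = 46, 60 − 28 = 32 or 60 − 56 = 4 days past the last active dose.
- Three months after the last active dose is 14 + 91 = day 105, 28 + 91 = day 119 or 56 + 91 = day 147.
- Less 61 days, this is 44, 58 or 86 days beyond the intent exclusion. The shortfall is smaller in the two short arms but present in all three.

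**Applying the rules to individual women**
- *Plans to conceive in month 3 or 4* (to about day 4 × 30.4 = 122). She is not excluded by section 5.1.2. Section 9.9 asks her to avoid pregnancy until at least day 140.
- *Uses a barrier only, for 60 days.* She meets the inclusion list, footnote 2 and section 6.8. She does not meet section 9.9, on number of methods or on duration.
- *Already on a hormonal method.* During treatment she adds a barrier under both rules; only section 9.9 carries this into the following three months.
- *On no method.* Section 9.9 supplies barriers but does not name the second component of a double method. Section 6.8 asks her not to start pills, injection, implant or patch during dosing.

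**The case against.** The strongest reply is that the texts do not contradict each other. Footnote 2 states a duty during treatment and never says that contraception may then stop. Section 9.9 states a longer and stricter duty for all women of childbearing age. A site that follows section 9.9 satisfies both. That is correct, so a reader who infers that no contraception duty exists in the three months after treatment goes further than the protocol allows. It does not rescue the intent exclusion, which is too short even at a site that follows section 9.9 to the letter.

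It can also be said that the counselling sentence serves the full-period requirement just before it. That is a fair reading of its purpose, but the risk it tells staff to explain is still confined to the treatment period.

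On method, a reader might infer that section 6.8 makes a double method impossible for a woman who starts with none. The protocol does not support that: an intrauterine device or a second barrier is not ruled out. What stands is that neither is named for her.

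Finally, the day counts run from the end of blinded dosing, although active drug ends at week 2 or 4 in two of the three arms. They measure a gap between rules, not drug exposure. No elimination time is given. The visits at months 1 and 4 and the pregnancy reporting in section 9.9 remain as safeguards. The consent form, which may state the three months, is not available here.

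**Conclusion.** The point holds as a mismatch that should be corrected. The eligibility text and section 9.9 set different pregnancy-prevention rules: about two months against about five from day 0, and one barrier with others optional against a double method. The part that depends least on interpretation is the pregnancy-intent exclusion, which leaves about 86 days (79 to 93) of the section 9.9 period uncovered. This assumes 91-day and 61-day conversions, a count from day 0, and a last dose within the week-8 window.

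The protocol does not show how much fetal risk, if any, falls in those days, and none is claimed. Nor is there any effect on endpoints, power or error rates. Eligibility and contraception rules belong in the protocol, so a statistical analysis plan would not be expected to settle them.

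**What to change.** 1. Extend the pregnancy-intent exclusion in section 5.1.2 to about five months from day 0: the 8-week blinded dosing period plus three months. Use the same length in all arms, because an arm-specific length would reveal the allocation.
2. Give footnote 2 the same period, with a cross-reference to section 9.9.
3. Extend the counselling sentence in section 9.9 to cover the three months after treatment.
4. State one method rule in both places, consistent with section 6.8. Women on an existing hormonal method or intrauterine device keep it and add a barrier. For women on no method, who are asked not to start hormonal drugs during dosing, name the accepted method or methods. An intrauterine device or a second barrier to accompany the supplied one are candidates that section 6.8 leaves open. If the supplied barrier alone is judged sufficient, section 9.9 must say so and drop the double requirement for these women.

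The cost is wording in footnote 2, one exclusion criterion and section 9.9, about three more months of barrier supplies, slightly narrower eligibility and a longer contraception request to participants.
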